#### 2.8.4 Other safety data

#### 2.8.4.1 ECG and cardiac imaging data

Summaries of ECG data will include on-treatment measurements, which are defined as measurements taken post-baseline but no later than 30 days after last dose of double-blind treatment for patients not entering the safety extension study (as described in Section 1.1) directly after the treatment period or not participating in the safety extension study. For patients entering the safety extension study directly after the treatment period, the on-treatment period lasts from the date of first administration of double-blind treatment to the date of the last actual administration of double-blind treatment. Triplicate ECGs and single ECGs will be performed at different visits specified in the assessment schedule table in the protocol. For the analysis of

For business use only

continuous ECG parameter involving triplicate ECGs, the mean value of the 3 ECG measurements will be used; for ECG interpretation, all findings of the 3 ECGs will be considered.

The number and percentage of patients with newly occurring or worsening notable Fridericia's QTc values will be summarized at any time on-treatment, considering all on-treatment data from scheduled, unscheduled and premature discontinuation visits. For derivation of notable values for the triplicate ECGs, the mean of the three ECGs will be used. Notable criteria are defined in Section 5.4.

The number and percentage of patients with ECG abnormalities will be summarized by evaluation type, abnormality finding, visit and time point. The baseline value is the last value prior to first dose of double-blind treatment.

ECG data of patients with notable Fridericia's QTc values will be listed.

#### 2.8.4.2 Vital signs

Summaries of vital signs data will include on-treatment measurements, which are defined as measurements taken post-baseline but no later than 30 days after last dose of double-blind treatment for patients not entering the safety extension study (as described in Section 1.1) directly after the treatment period or not participating in the safety extension study. For patients entering the safety extension study directly after the treatment period, the on-treatment period lasts from the date of first administration of double-blind treatment to the date of the last actual administration of double-blind treatment.

The number and percentage of patients with newly occurring or worsening notable vital sign values will be summarized at any time on-treatment, considering all on-treatment data from scheduled, unscheduled and premature discontinuation visits. Notable criteria are defined in Section 5.4.

The baseline value is the last value prior to first dose of double-blind treatment.

Vital sign data of patients with notable values will be listed.

#### 2.8.5 Immunogenicity

All immunogenicity analysis will be conducted for each safety set and reported separately other than in the CSR.

#### 2.8.5.1 Immunogenicity (IG) analysis sets

The Immunogenicity prevalence set includes all subjects in the Safety set with a non-missing baseline ADA sample **or** at least one non-missing post-baseline ADA sample. The Immunogenicity incidence set includes all subjects in the Immunogenicity prevalence set with a non-missing baseline ADA sample **and** at least one non-missing post-baseline ADA sample.

Any ADA sample collected beyond 150 days of the last dose of CSJ117 will not be used for summaries or derivations and will only be included in the listing

The following definitions apply only to non-missing samples:

Novartis SAP

- *ADA-negative sample*: Sample where assay result is 'NEGATIVE' and CSJ117 concentration at the time of ADA sample collection is ≤ the drug tolerance level (10 microgram/mL)
- *ADA-positive sample*: Sample where assay result is 'POSITIVE'
- *ADA-inconclusive sample:* Sample where assay is ADA negative and CSJ117 PK concentration at the time of ADA sample collection is > the drug tolerance level (10 microgram/mL) or missing

The following definitions apply only to post-baseline ADA-positive samples with a corresponding non-missing baseline sample. To be classified as *treatment-boosted* or *treatment-unaffected*, both the post-baseline and baseline titer must be non-missing.

- *treatment-induced ADA-positive sample:* ADA-positive sample post-baseline with ADA-negative sample at baseline
- *treatment-boosted ADA-positive sample:* ADA-positive sample post-baseline with titer that is at least 3 fold change greater than the ADA-positive baseline titer
- *treatment-unaffected ADA-positive sample*: ADA-positive sample post-baseline with titer that is less than 3 fold change greater than the ADA-positive baseline titer

The following summaries of ADA sample status (n and %) will be provided using the *Immunogenicity prevalence set*: ADA-positive samples (i.e. ADA prevalence) both overall, by treatment and by time point (including baseline). For summaries by time point, the denominator is the number of subjects at that time point with a non-missing sample.

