8.6.2 Pharmacokinetics

PK samples will be collected at the visits defined in the assessment schedule (Table 8-1). Follow instructions outlined in the laboratory manual regarding sample collection, numbering, processing, and shipment.

The number of samples/blood draws collected will not exceed those stated in the protocol.

Pharmacokinetic (PK) samples will be obtained but only evaluated in all subjects at all dose levels except the placebo group.

Total CSJ117 will be determined by a validated immunoassay method; the anticipated Lower Limit of Quantification (LLOQ) is 3 ng/mL.

Concentrations will be expressed in mass per volume units (ng/mL)

Concentrations below the LLOQ will be reported as "zero" and missing data will be labeled as such in the Bioanalytical Data Report.

The following pharmacokinetic parameters will be determined using the actual recorded sampling times and non-compartmental method(s) with Phoenix WinNonlin (Version 6.4 or higher): Ctrough, Racc, and T1/2 from the serum concentration-time data. Additional pharmacokinetic parameters may be calculated as necessary.

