8.6.5 Other Assessments

8.6.5.1 Immunogenicity

Immunogenicity (IG) blood samples for ADA will be obtained and evaluated in all subjects at all dose levels, including the placebo group, at the timepoints defined in the Assessment schedule (Table 8-1). In case of positive immunogenicity, backup of previous pre-dose PK samples could be used to better characterize the onset of immunogenicity response.

Immunogenicity analytical method(s)

A validated bridging electrochemiluminescence immunoassay (ECLIA) will be used for the detection of potential anti-CSJ117 antibodies in serum, including 3 tiers of screening, confirmation and titration.

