#### 2.8.5.2 Subject ADA status

Any ADA sample collected beyond 150 days of the last dose of CSJ117 will not be used for summaries or derivations and will only be included in the listing.

Subject ADA status is defined as follows:

- *Treatment-induced ADA-positive subject*: subject with ADA-negative sample at baseline and at least one treatment-induced ADA-positive sample
- *Treatment-boosted ADA-positive subject*: subject with ADA-positive sample at baseline and at least one treatment-boosted ADA-positive sample
- *Treatment-unaffected ADA-positive subject*: subject with ADA-positive sample at baseline, no treatment-boosted ADA-positive samples, and at least one treatment-unaffected ADA-positive sample
- *Treatment-reduced ADA-positive subject*: subject with ADA-positive sample at baseline and at least one non-missing post baseline sample, all of which are ADA-negative samples
- *ADA-negative subject*: subject with ADA-negative sample at baseline and at least one non-missing post baseline sample, all of which are ADA-negative samples
- *Inconclusive subject*: subject who does not qualify for any of the above definitions or a subject for which the baseline sample is missing and CSJ117 PK concentration at the

time of ADA sample collection is > the drug tolerance level (10 microgram/mL) or missing

-Following data with number and percentage of subjects will be reported/tabulated by treatment group and during overall study duration. The following summaries of ADA subject status (n and %) will be provided using the *Immunogenicity incidence set* (for % the denominator is the number of subjects in the *Immunogenicity incidence set* unless otherwise specified). :

- ADA negative
- ADA positive (prevalence set)
  - Total ADA positive with no boost
- ADA inconclusive (exposure above drug tolerance according to validated method)
- Missing ADA data at pre-dose
- Missing ADA data at post-dose (Number of patients with atleast 1 missing sample)

Following data with number and percentage of subjects will be reported/tabulated by treatment group for the whole study period:

Pre-dose ADA positive

boosted: boosted is defined as ADA positive at pre-dose, and post dose titer values increase from pre-dose by more than 3-fold at any time point (Treatment-boosted ADA-positive subjects; for % the denominator is the number of subjects with ADA-positive sample at baseline)

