#### Pre-dose ADA negative

- induced: ADA-positive sample post-baseline with ADA-negative sample at baseline (Treatment-induced ADA-positive subjects; for % the denominator is the number of subjects with ADA-negative sample at baseline)
  - Transient
  - Persistent

Overall ADA incidence (combined results of treatment-boosted and induced)

For induced ADA positive, summaries will also be provided based on the persistent or transient ADA status. The definition of persistent and transient is as follows.

Persistent ADA: a) Treatment-induced ADA detected at two or more sampling time points during the treatment (including follow-up period if any), where the first and last ADA-positive samples (irrespective of any negative samples in between) are separated by a period of 16 weeks or longer or b) Treatment-induced ADA incidence only in the last sampling time point of the treatment or follow up observation period\_or at a sampling time point within less than 16 weeks before an ADA-negative last sample.

Transient ADA: a) Treatment-induced ADA detected only at -one sampling time point during the treatment or follow-up observation period (excluding the last sampling time point) and that

For business use only

Page 29 of 41 CCSJ117A12201C

sampling point is 16 weeks or more before an ADA negative last sample or b) Treatmentinduced ADA detected at two or more sampling time points during the treatment (including follow-up period if any), where the first and last ADA-positive samples (irrespective of any negative samples in between) are separated by a period less than 16 weeks, and the subject's last sampling time is ADA Negative.

ADA titer kinetics will be summarized by treatment group with data reported as boxplot (titer range, Q1, Median (Q2), Q3, and outliers) of ADA titer at each time point for each treatment group up to Week 24. The plot will include total subjects, number of subjects with positive ADA, and % of subjects with positive ADA at each time point. Please see example below from Shankar et al.

[figure not shown]

Fig. 3. ADA titer kinetics. This plot of titers over time in a study is useful in determining whether the ADA levels tend to change over time during the treatment. Each *box plot* represents the titer range, Q1, Median (Q2), Q3, excluding outliers (*asterisks*)

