#### 2.9 Pharmacokinetic endpoints

Pharmacokinetic analysis will be conducted and reported separately other than in the CSR.

CSJ117 plasma concentration data will be listed by treatment, subject, and visit/sampling time point. Descriptive summary statistics will be provided by treatment and visit/sampling time point, including the frequency (n, %) of concentrations below the lower limit of quantification (LLOQ) and reported as zero. Summary statistics will include mean (arithmetic and geometric), standard deviation, coefficient of variation (arithmetic and geometric), median, minimum, and

maximum. Concentrations below LLOQ will be treated as zero in summary statistics and for PK parameter calculations. If at a single time point a substantial number of concentrations are below LLOQ, they may be substituted with a pre-defined value, such as ½ LLOQ for calculation of PK parameters.

Summary serum concentrations would be plotted by visit. Dose proportionality of serum concentrations will be assessed. .

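### Under the SAP's ADA rules every assay-negative placebo sample is inconclusive, so ADA-negative status, treatment-induced incidence and a valid overall incidence cannot be derived for placebo

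*SAP*

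**What the plan says.** **What is measured.** Protocol 8.6.5.1 says that ADA samples "will be obtained and evaluated in all subjects at all dose levels, including the placebo group". Protocol 8.6.2 says that PK "samples will be obtained but only evaluated in all subjects at all dose levels except the placebo group".

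**Sample rules (SAP 2.8.5.1).** A positive assay result makes a sample ADA-positive, with no PK condition. A negative result makes it ADA-negative only if the concentration is at or below 10 µg/mL. A negative result is inconclusive if the "CSJ117 PK concentration at the time of ADA sample collection is > the drug tolerance level (10 microgram/mL) or missing".

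**Subject rules (SAP 2.8.5.2).** A treatment-induced subject is a "subject with ADA-negative sample at baseline and at least one treatment-induced ADA-positive sample". For the treatment-induced percentage, "the denominator is the number of subjects with ADA-negative sample at baseline". ADA-negative and treatment-reduced subjects both need post-baseline samples that are all ADA-negative. Anyone who fits no category is inconclusive. The tables are by treatment group and include the rows "ADA inconclusive (exposure above drug tolerance according to validated method" and "Overall ADA incidence (combined results of treatment-boosted and induced".

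**Zero rule (SAP 2.9).** "Concentrations below LLOQ will be treated as zero in summary statistics" and in PK parameter calculations. Protocol 8.6.2 likewise reports values below LLOQ as zero, and separately has missing data labelled as missing.

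**The concern.** The rule for inconclusive samples guards against a false negative caused by circulating drug. Placebo patients have no circulating drug, yet the rule captures all their assay-negative samples because the concentration that would clear them is never determined. Neither document exempts placebo or sets its concentration to zero.

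Two outputs suffer. The placebo column of the subject-status table would put most patients in a row described as exposure above drug tolerance, which cannot be true of someone given no CSJ117. That label also disagrees with the definition, which adds missing concentrations. In addition, overall ADA incidence would be built from different components in the two groups, always understating placebo. Immunogenicity remains a secondary objective in SAP 1.2, and placebo is the reference for judging how much apparent seroconversion occurs without drug.

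**Working it through.** The plan states no ADA rate or incidence for this trial, so there is no figure of its own to reproduce. The main result is logical; the arithmetic only sizes it.

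**Step 1: apply the rules to placebo**

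| Category | Needs | Available on placebo? |
|---|---|---|
| ADA-positive sample | positive assay | yes |
| ADA-negative sample | negative assay and concentration ≤ 10 µg/mL | never: no concentration |
| Inconclusive sample | negative assay and concentration > 10 µg/mL or missing | every assay-negative sample |
| Treatment-induced subject | ADA-negative baseline | never |
| Treatment-induced denominator | ADA-negative baselines | 0, so the percentage is 0/0 |
| ADA-negative subject | ADA-negative baseline and post-baseline samples | never |
| Treatment-reduced subject | positive baseline, then all ADA-negative samples | never |
| Boosted or unaffected subject | positive baseline and positive post-baseline sample, with titers | yes |

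The zeros hold for any assay data. The transient/persistent split of induced ADA is lost as well.

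**Step 2: illustration**

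The rules were coded literally and applied to 74 placebo patients with assumed assay patterns: 60 negative throughout, 5 negative turning positive, 4 positive unchanged, 1 positive boosted, 4 positive turning negative.

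| | Concentration missing (as written) | Concentration taken as 0 |
|---|---|---|
| ADA-negative | 0 | 60 |
| Treatment-induced | 0/0 | 5/65 |
| Boosted | 1 | 1 |
| Unaffected | 4 | 4 |
| Reduced | 0 | 4 |
| Inconclusive | 69 | 0 |
| Overall incidence | 1/74 | 6/74 |

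**Step 3: patients affected**

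- Enrolment is 335 (SAP 1.1) and allocation 2:1:1:1:2:2, so placebo is 335 × 2/9 = 74.4, about 74 if the ratio was achieved.
- Pre-existing ADA: 2 of 24 subjects in study CSJ117X1101 (Protocol 4.5), p = 2/24 = 8.3%, exact 95% CI 1.0% to 27.0%.
- Assay-negative at baseline on placebo: 74 × (1 − 0.083) = 67.8, about 68 (54 to 73 over the CI). All become inconclusive, so the treatment-induced denominator falls from about 68 to 0.

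**Step 4: distortion of overall incidence**

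Let the boosted rate b among baseline-positive patients and the induced rate i among baseline-negative patients be the same in every arm.

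- Active: p·b + (1 − p)·i
- Placebo as written: p·b
- Spurious difference: (1 − p)·i = 0.917·i

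| Assumed i | Spurious difference (percentage points) | Placebo conversions not counted (67.8 × i) |
|---|---|---|
| 2% | 1.8 | 1.4 |
| 5% | 4.6 | 3.4 |
| 10% | 9.2 | 6.8 |

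Over the CI for p and these values of i, the difference runs from 1.5 to 9.9 points.

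**The case against.** **An unevaluated placebo concentration may not be meant as missing.** SAP 2.8.5.2 closes by saying that systemic exposure is measured alongside ADA, without excluding placebo, and placebo PK samples are drawn. The row label mentions only exposure above tolerance, and the 150-day sample cut-off runs from the last CSJ117 dose. The section looks written with treated patients in mind, and an analyst might simply take placebo as zero. That is a fair reading of intent, but the general sentence on exposure does not override the protocol's specific exclusion of placebo from PK evaluation. The zero rules cover measured values below LLOQ. Using zero for placebo would depart from an explicit clause without being written down.

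**The practical effect may be small.** In study CSJ117X2201, 13 of 15 CSJ117-treated patients (87%) developed ADA (Protocol 4.5). Against an active rate of that order, a few uncounted placebo conversions would not change the interpretation. The equal-rates scenario uses assumed conversion rates and a baseline rate from 24 healthy Japanese men. This limits the impact and stands, but the misclassification does not depend on those rates.

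**The outputs are descriptive.** There is no between-arm test, immunogenicity is reported outside the CSR, and SAP Section 4 drops the analysis of ADA impact. Placebo seroconversion can still be seen in prevalence by time point, titer plots and listings, and a 0/0 beside a very large inconclusive row would be noticed. All of this is true and keeps the point at a moderate level. Section 4 does not, however, remove the by-arm status and incidence tables.

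**Conclusion.** The concern holds. As written, the rules give zero ADA-negative samples on placebo, a treatment-induced percentage of 0/0, and an overall incidence that omits every placebo seroconversion. Those table entries would be wrong by construction, in a direction that makes active look worse.

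The logical result rests on one reading: that a concentration never evaluated is missing. That is the plain sense of the text. The size (about 68 of 74 placebo patients, and 1.8 to 9.2 percentage points) also assumes that the planned allocation was achieved, that the 2-in-24 baseline rate applies, and that conversion of 2% to 10% is equal across arms.

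ADA prevalence by arm and time point, titers, the boosted rate among baseline-positive patients and the primary FEV1 analysis are not affected. Baseline samples and the three-tier assay still address pre-existing reactivity and false positives. The same clause makes an active-arm baseline sample inconclusive if its pre-dose PK result is missing; how often that happens is not known. This should be corrected before the immunogenicity tables are produced.

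**What to change.** Add to SAP 2.8.5.1 and 2.8.5.2:

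> For all samples taken before the first dose of double-blind treatment, and for all samples from placebo patients with no documented receipt of CSJ117, a NEGATIVE assay result is an ADA-negative sample regardless of whether a CSJ117 concentration is available.

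Keep the concentration condition for post-dose samples from anyone who received CSJ117. That includes patients who stay in the placebo group of the Safety Set under SAP 2.2 after also receiving CSJ117; if they have no PK result, inconclusive is the right status and no extra assay is needed.

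Split the inconclusive table row in two: concentration above drug tolerance, and concentration missing. The label then matches the definition, and missing PK in the active arms becomes visible.

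The cost is one sentence, one extra table row and one condition in the derivation code, with no new samples or assays.

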#### 2.8.5.2 Subject ADA status

Any ADA sample collected beyond 150 days of the last dose of CSJ117 will not be used for summaries or derivations and will only be included in the listing.

Subject ADA status is defined as follows:

- *Treatment-induced ADA-positive subject*: subject with ADA-negative sample at baseline and at least one treatment-induced ADA-positive sample
- *Treatment-boosted ADA-positive subject*: subject with ADA-positive sample at baseline and at least one treatment-boosted ADA-positive sample
- *Treatment-unaffected ADA-positive subject*: subject with ADA-positive sample at baseline, no treatment-boosted ADA-positive samples, and at least one treatment-unaffected ADA-positive sample
- *Treatment-reduced ADA-positive subject*: subject with ADA-positive sample at baseline and at least one non-missing post baseline sample, all of which are ADA-negative samples
- *ADA-negative subject*: subject with ADA-negative sample at baseline and at least one non-missing post baseline sample, all of which are ADA-negative samples
- *Inconclusive subject*: subject who does not qualify for any of the above definitions or a subject for which the baseline sample is missing and CSJ117 PK concentration at the

time of ADA sample collection is > the drug tolerance level (10 microgram/mL) or missing

-Following data with number and percentage of subjects will be reported/tabulated by treatment group and during overall study duration. The following summaries of ADA subject status (n and %) will be provided using the *Immunogenicity incidence set* (for % the denominator is the number of subjects in the *Immunogenicity incidence set* unless otherwise specified). :

- ADA negative
- ADA positive (prevalence set)
  - Total ADA positive with no boost
- ADA inconclusive (exposure above drug tolerance according to validated method)
- Missing ADA data at pre-dose
- Missing ADA data at post-dose (Number of patients with atleast 1 missing sample)

Following data with number and percentage of subjects will be reported/tabulated by treatment group for the whole study period:

Pre-dose ADA positive

boosted: boosted is defined as ADA positive at pre-dose, and post dose titer values increase from pre-dose by more than 3-fold at any time point (Treatment-boosted ADA-positive subjects; for % the denominator is the number of subjects with ADA-positive sample at baseline)

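### The subject ADA status table is built on a set that requires a baseline sample, so its row for missing pre-dose data can only be zero, and the denominator of its ADA-positive row is unclear

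*SAP*

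**What the plan says.** SAP 2.8.5.1 defines two immunogenicity sets.

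- The prevalence set is "all subjects in the Safety set with a non-missing baseline ADA sample or at least one non-missing post-baseline ADA sample".
- The incidence set is "all subjects in the Immunogenicity prevalence set with a non-missing baseline ADA sample and at least one non-missing post-baseline ADA sample".

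SAP 2.8.5.2 places the subject-status summaries on the incidence set and adds that "for % the denominator is the number of subjects in the *Immunogenicity incidence set* unless otherwise specified". The rows then listed include ADA negative, a row that begins "ADA positive (prevalence set", ADA inconclusive, "Missing ADA data at pre-dose", and a post-dose missing row that counts patients with at least one missing sample.

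The same section classes as inconclusive, among others, a subject who has no baseline sample and whose drug concentration at ADA sampling is above the tolerance level or missing. For the boosted and induced rows that follow, it writes out the denominators: baseline-positive and baseline-negative subjects respectively.

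**The concern.** A table that reports how much ADA data is missing should be run on a population in which data can be missing. Here the population is selected on having the data. A reader of the finished table would see no missing baselines in any arm and could take that as evidence of complete sampling.

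The ADA-positive row raises a separate question. Its label names one set while the table as a whole uses a smaller one, and the row does not say which set supplies the percentage.

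Immunogenicity is a secondary objective (Protocol Table 2-1; SAP 1.2). Protocol 4.5 reports that 13 of 15 patients treated with CSJ117 in the earlier mild-asthma study developed ADA. Counts and rates in this table are therefore likely to be read with interest.

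**Working it through.** The documents give no figure for this table, so there is nothing of the plan's to reproduce. The check has two parts.

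**1. What the set definitions allow**

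*Meaning of pre-dose.* In SAP 2.8.5.2, "boosted is defined as ADA positive at pre-dose, and post dose titer values increase from pre-dose", and the percentage for that row is taken over subjects with an ADA-positive baseline sample. Pre-dose therefore means baseline in this section.

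*Inputs.* One baseline ADA sample and eight post-baseline samples (Weeks 2, 4, 8, 12, 14, 16, 20 and 24; Protocol Table 8-1). Each is present or missing, giving 2^9 = 512 availability patterns.

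- Prevalence set (baseline or any post-baseline sample): 512 − 1 = 511 patterns, of which 2^8 − 1 = 255 have no baseline sample.
- Incidence set (baseline and any post-baseline sample): 2^8 − 1 = 255 patterns, of which 0 have no baseline sample.
- Incidence set with at least one post-baseline sample missing: 255 − 1 = 254 patterns. With all post-baseline samples missing: 0 patterns.

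Three results follow.

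- The pre-dose missing row is zero by construction.
- The post-dose missing row can be non-zero, but it leaves out the subjects with the most missing data.
- The missing-baseline clause of the inconclusive definition has nobody to act on in this table.

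**2. The ADA-positive row under each reading**

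*Inputs.*

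- Actual enrolment is 335 and allocation is 2:1:1:1:2:2 (SAP 1.1), so a double-weight arm has about 335 × 2/9 = 74 subjects.
- Assumed: 2%, 5% or 10% of the arm lack a baseline sample, which rounds to 1, 4 or 7 subjects, and everyone has a post-baseline sample. The prevalence set is then 74 and the incidence set 73, 70 or 67.
- ADA rate: 13/15 (the earlier study) or an assumed 30%, giving 64 or 22 positive subjects in the arm.

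*Formulas.* Consistent reading = positives ÷ prevalence set. Mixed reading = prevalence-set positives ÷ incidence set. The ratio of mixed to consistent is prevalence set ÷ incidence set.

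| Baselines missing | Ratio | Rate 13/15: consistent | Rate 13/15: mixed | Rate 30%: consistent | Rate 30%: mixed |
|---|---|---|---|---|---|
| 1 of 74 | 74/73 = 1.014 | 64/74 = 86.5% | 64/73 = 87.7% | 22/74 = 29.7% | 22/73 = 30.1% |
| 4 of 74 | 74/70 = 1.057 | 86.5% | 64/70 = 91.4% | 29.7% | 22/70 = 31.4% |
| 7 of 74 | 74/67 = 1.104 | 86.5% | 64/67 = 95.5% | 29.7% | 22/67 = 32.8% |

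The mixed reading overstates by between 30.1 − 29.7 = 0.4 and 95.5 − 86.5 = 9.0 percentage points. On the same assumptions the pre-dose missing row would show 1, 4 or 7 subjects on the Safety Set, against 0 as written.

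**The case against.** The strongest reply concerns the ADA-positive row. The default denominator carries a proviso that yields to any other specification, and the prevalence set named in the row label can be read as exactly that. On this reading numerator and denominator agree and nothing is inflated. A reader might infer from the layout that the SAP does divide a prevalence-set count by the incidence-set total. The documents do not establish this. Against the benign reading, where the SAP replaces the default for the boosted and induced rows it says so in words, and here it does not. What remains is an ambiguity.

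A second reply is that little information is lost. SAP 2.8.5.1 also gives ADA prevalence on the prevalence set, overall, by treatment and by time point including baseline, and the time-point denominator is the number with a non-missing sample. Subtracting the baseline denominator from the Safety Set size recovers the missing count. SAP 2.8.5.2 also lists all titers. This stands, and it limits the harm. It does not make a row that can only read zero correct.

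Third, the sizes above are assumed. The baseline ADA sample is scheduled about an hour before the first dose, together with the other blood samples (Protocol Table 16-3), and nothing in the documents suggests a missing rate near 10%. That also stands. Nor would arms with scattered missing post-baseline samples be affected: a subject leaves the incidence set only by lacking a baseline sample or every post-baseline sample.

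Finally, these are descriptive tables. SAP 1.2 and 2.8.5 report immunogenicity outside the CSR, and SAP 4 drops the analysis of ADA impact on efficacy and safety. No test or primary estimate depends on them.

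**Conclusion.** The point about missing data holds on the SAP's own definitions and needs no assumption. The pre-dose missing row is always zero, subjects with no post-baseline sample cannot enter the post-dose missing row, and the missing-baseline part of the inconclusive class is empty in this table. These are stated rules that give wrong counts.

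For the ADA-positive row, the supportable conclusion is that its denominator is unclear. The overstatement of 0.4 to 9 points arises only under the mixed reading. It also rests on an arm of 74, assumed missing-baseline fractions of 2% to 10%, and ADA rates of 30% to 13/15. It should not be quoted as a bias in the plan.

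The consequence is confined to descriptive immunogenicity tables outside the CSR. The primary analysis is untouched. The correction is still worth making, because it changes reported figures for a secondary objective at almost no cost.

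**What to change.** In SAP 2.8.5.2, assign a set to each row.

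- **Both missing-data rows:** use the Safety Set. Count a post-dose sample as missing only if it was scheduled for that patient. Extension entrants finish this study at Week 12 (Protocol 9.2), and patients stopped by the early termination have an 8-week follow-up (SAP 1.1). Without this limit, the samples they were never due to give could be counted as missing.
- **ADA positive:** state the prevalence set as both numerator and denominator, and say whether the no-boost sub-row follows it.
- **ADA inconclusive:** name a set that admits subjects without a baseline sample, so that the definition can operate.
- **ADA negative and overall incidence:** keep the incidence set.
- **Boosted and induced:** keep the existing baseline-positive and baseline-negative denominators.

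The cost is a few lines of SAP text and a table-shell footnote. No new data are needed.
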